10.1. Definition of Serious Adverse Events

A serious adverse event is any untoward medical occurrence that:

results in death

is life-threatening

requires inpatient hospitalisation or prolongation of existing hospitalisation

· results in persistent or significant disability/incapacity

consists of a congenital anomaly or birth defect

Other 'important medical events' may also be considered a serious adverse event when, based upon

appropriate medical judgement, the event may jeopardise the participant and may require medical or

surgical intervention to prevent one of the outcomes listed above.

NOTE: The term "life-threatening" in the definition of "serious" refers to an event in which the participant

was at risk of death at the time of the event; it does not refer to an event which hypothetically might have

caused death if it were more severe.

11. MAIN STATISTICAL ANALYSIS

11.1. Statistical Analysis Plan (SAP) for the trial analyses

The statistical aspects of the trial analyses are summarised here (Section 11.1-11.8) with details of the trial

analyses fully described in a statistical analysis plan that will be finalised before the final analysis takes

place and agreed by the Trial Steering Committee (TSC). Information on the imaging and diagnostic

uncertainty statistical analyses and Health economic analyses are summarised in Sections 12.1 and 12.2

below. A single main set of analyses will be performed at the end of the follow-up. The main analyses will

be according to randomised groups irrespective of non-compliance, "as randomised" population (See

Section 11.4) and based upon the data up to and including the 24 months timepoint. Details of the 5-year

HES analysis are given in Section 12.4.

Analyses will be carried out using Stata (Stata: Release 15. Statistical Software. College Station, TX:

StataCorp LP; 2017.15).

Clinical Research Protocol Template version 15.0

11.2. Description of the Statistical Methods

Baseline, treatment, study process, and outcomes data will be summarised using appropriate statistical

summarises (e.g. number of observations and percentages for binary measures). The primary outcome will

be compared using generalised estimating equation (GEE) model with adjustment for the randomisation

variables (age, type of tear & site), baseline OSS and time point using fixed effects. A secondary unadjusted

analysis will also be carried out by an independent t-test. Secondary outcomes will be analysed using

generalised linear multilevel models with adjustment for minimisation and baseline variables as

appropriate. Exploratory subgroup analyses will explore the possible treatment effect modification of

patient age and type of tear, through the use of treatment by factor interaction, and will be interpreted

cautiously.

The impact of missing data and non-compliance on the findings will also be explored in sensitivity analyses

of the primary outcome utilising appropriate methods (e.g. the rctmiss Stata command for assessing the

impact of missing not at random for OSS using a pattern mixed-model based approach) (30) and complier

average causal effect (CACE) (31) type approaches respectively.

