## 6. OBJECTIVES AND OUTCOME MEASURES

Research Question: In patients with suspected PTT listed for arthroscopic surgery, is ADAR more beneficial than ADO as measured by pain reduction and functional restoration at 24 months post operation?

Objectives	Outcome Measures	Timepoint(s)			
Primary Objective	Primary Objective				
To assess and compare patient reported pain and function outcome following arthroscopic debridement and repair of PTT versus arthroscopic debridement only	Oxford Shoulder Score	24 months (+ Baseline)			

Secondary Objectives					
To assess and compare early 1. patient reported pain and function outcome	Oxford Shoulder Score	6 and 12 months, and 5 years (+Baseline)			
To assess and compare patients' quality of life	EuroQol EQ-5D-5L	6, 12, and 24 months and 5 years (+Baseline)			
3. To assess and compare patient resource use	Health resource use	6, 12, and 24 months			
4. To assess and compare patient satisfaction and perceptions	Patient Satisfaction and perception questions	6, 12 and 24 months and 5 years			
5. To assess and compare tear progression	Progression to full thickness cuff tears as assessed by MRI imaging	24 months			
To assess and compare long term health care usage, complications, further surgery, patient reported pain and function and quality of life for randomised patients.	Readmission for further surgery and associated costs as assessed by routinely collected observational hospital data (HES)	5 years			
Exploratory Objectives					
To optimise the accuracy of MRI and USS imaging in diagnosing PTTs	Comparison of imaging reports to arthroscopic findings	During recruitment phase			
2. To assess the long-term health care usage, complications, further surgery, for the non-randomised patients	Readmission for further surgery and associated costs as assessed by routinely collected observational hospital data (HES)	5 years			
QRI Objectives					
Refer to section 7.2.1					

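### The primary GEE lists time point only as a fixed effect and names no 24-month contrast; fitted as listed, it estimates a time-averaged difference, not the 24-month Oxford Shoulder Score difference that is the primary outcome

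*Protocol*

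**What the plan says.** **Target.** Section 6 asks "is ADAR more beneficial than ADO as measured by pain reduction and functional restoration at 24 months post operation". The synopsis and the objectives table give 24 months as the only primary time point. The earlier OSS scores belong to a secondary objective, timed at "6 and 12 months, and 5 years (+Baseline").

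**Model.** For the primary outcome, section 11.2 specifies a GEE. Its listed terms are the minimisation factors, the baseline score and time: "variables (age, type of tear & site), baseline OSS and time point using fixed effects". An independent t-test serves as the unadjusted secondary analysis. Other outcomes go to a different model class, multilevel generalised linear models.

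**Interactions.** The only ones named in section 11.2 are the exploratory subgroup terms: "patient age and type of tear, through the use of treatment by factor interaction, and will be interpreted" with caution.

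**Data window and detail.** Section 11.1 bases the main analyses on "data up to and including the 24 months timepoint". It presents section 11 as a summary and leaves the full description to the SAP: "analyses fully described in a statistical analysis plan that will be finalised before the final analysis takes".

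**The concern.** A time-point covariate has a function only if each participant can contribute more than one follow-up score. Baseline OSS is a covariate in this model, and the data window excludes the 5-year score. What remains from the schedule in Appendix A is 6, 12 and 24 months.

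With time as a main effect only, the model assumes the same treatment difference at every visit and returns one coefficient for it. If the true difference changes over time, that coefficient answers a different question from the one in section 6. The error can run both ways: a benefit of repair that emerges late is diluted by the earlier visits, and a benefit that has gone by 24 months can still produce a significant primary result.

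The protocol gives no reason to take the effect as constant. It treats early OSS as a separate objective. The lay summary asks whether repair gives lasting benefit and prevents larger tears, and section 5 distinguishes short-to-medium-term effects on pain and disability from longer-term effects.

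**Working it through.** **1. The plan's own sample size (section 11.3).** Inputs: difference 4, SD 9, two-sided 5%, 90% power, 20% attrition, 30% ineligible in theatre.

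- n per group = 2(1.960 + 1.282)² × 9² / 4² ≈ 106.4, so 107 by normal approximation. The t-test version gives 107.36, so 108, as stated.
- 108 / 0.8 = 135 per group, 270 in total; 270 / 0.7 = 385.7, so 386.

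All figures are reproduced. The calculation is a two-group comparison at a single time point.

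**2. What the listed model estimates.** Assume equal SDs of 9 at each visit, a common correlation ρ between visits, and complete data on 108 per group.

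- Time-averaged coefficient: (d6 + d12 + d24) / 3, with standard error 9 × √[(1 + 2ρ)/3] × √(2/108).
- 24-month contrast: d24, with standard error 9 × √(2/108) = 1.225.
- Power ≈ Φ(|effect| / SE − 1.96).

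Example at ρ = 0.5 with differences 0/2/4: the average is 2.0 and its SE is 9 × 0.816 × 0.136 = 1.00, so power = Φ(2.00 − 1.96) = 52%. For the 24-month contrast, power = Φ(4/1.225 − 1.96) = Φ(1.31) = 90%.

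The profiles and ρ below are assumptions; the protocol gives neither. Cells show the probability of a significant result.

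| True difference at 6/12/24 months | Average | ρ = 0.3 | ρ = 0.5 | ρ = 0.7 | 24-month contrast |
|---|---|---|---|---|---|
| 0/2/4 | 2.0 | 61% | 52% | 45% | 90% |
| 2/3/4 | 3.0 | 92% | 85% | 78% | 90% |
| −2/1/4 | 1.0 | 20% | 17% | 15% | 90% |
| 4/2/0 | 2.0 | 61% | 52% | 45% | 5% |
| 4/4/4 | 4.0 | 99% | 98% | 96% | 90% |

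**3. Check by simulation.** Both simulations used 135 per group, SD 9, an exchangeable working correlation, robust standard errors and adjustment for baseline OSS. The correlations and the 6- and 12-month losses are assumed; the 20% loss at 24 months follows section 11.3.

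- A: 600 trials per profile; correlation 0.6 between follow-ups and 0.4 with baseline; losses 8/13/20%.
- B: 400 trials per profile; correlation 0.5 throughout; losses 10/15/20%.

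| Profile | Listed model, A | Listed model, B | 24-month contrast, A | 24-month contrast, B |
|---|---|---|---|---|
| 0/2/4 | 1.9; 55% | 1.90; 70% | 4.0; 95% | 3.98; 96% |
| −2/1/4 | 0.8; 17% | 0.84; 20% | not recorded | 4.01; 97% |
| 4/2/0 | 72% significant | 2.16; 82% | 7% | 0.02; 5.5% |
| 4/4/4 | 4.0 | 3.99; 100% | 4.0 | 3.95; 98% |

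Entries are mean estimate; proportion significant, where both were recorded. Simulated rates tend to exceed the formula rates, chiefly because baseline adjustment reduces the error variance. The mean estimates stay close to the equal-weight averages: 1.90 against 2.0, and 2.16 against 2.0.

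**The case against.** The strongest reply is that section 11.2 gives a list of adjustment covariates in a summary, not a full model. It does not state the visits entered, the working correlation or the contrast reported. An interaction with treatment is not an adjustment variable, so leaving it off the list does not exclude it. Section 11.1 defers detail to the SAP, which is not among the documents at hand. The primary outcome is defined at 24 months, so comparing the primary outcome can be read as the 24-month comparison. The t-test takes one value per participant, most naturally the 24-month score.

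Much of this stands. A reader might infer that the sponsor has fixed a main-effects model and will report a time-averaged difference as the 24-month result. The protocol does not say so: the visits are inferred, the interaction is left open, and a 24-month difference would probably appear through the t-test. What does not fall away is that the terms actually listed, if followed, do not deliver the stated primary outcome, while the same paragraph does name interactions where it wants them. The t-test is only a secondary, unadjusted analysis.

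Three other inferences go too far:

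- **Strong weighting towards early visits.** The shift depends on the assumed missingness and was slight in the simulations.
- **Analysing 6- and 12-month OSS in a different model is an error.** The multilevel wording is generic, and using the same scores in two models is a matter of preference.
- **One firm false-positive rate.** For 4/2/0 the figure runs from 45% to 82% across the assumptions.

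**Conclusion.** The point holds as a mismatch between the listed terms of the primary model and the stated primary outcome. It is not proof that the wrong quantity will be reported. Read as written, and taking the 6-, 12- and 24-month scores as the data, the coefficient is an approximately equal-weight average that matches the 24-month effect only under a constant effect.

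The size depends on profiles and correlations that the protocol does not supply. With 0/2/4 the estimate is about half the 24-month difference, and power falls to 45–61% by formula, or 55% and 70% in the two simulations. With 4/2/0 a significant primary result would be common despite no 24-month effect. With 4/4/4 there is no harm. The sample size calculation is correct. Because the ambiguity concerns which quantity decides the trial, it should be settled before outcome data are compared by arm.

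**What to change.** In section 11.2, carried into the SAP: state that the GEE uses the 6-, 12- and 24-month OSS, add a treatment-by-time-point interaction, and name the adjusted treatment contrast at 24 months as the primary estimate. If the SAP already does this, align section 11.2 with it.

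The cost is about one sentence, and 270 randomised participants still suffice. The 24-month contrast had about 90% power by formula and 95–98% in the simulations when the true 24-month difference was 4. The downside is precision if the effect really is constant: at ρ = 0.5 the formula standard error is 1.22 against 1.00 for the pooled coefficient, and power is 90% against 98%.

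A baseline-by-time term, and taking the 6- and 12-month secondary contrasts from the same model, are optional.

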11.3. Sample Size Determination

A recent systematic review of shoulder PROMs found a minimum important difference (MID) in the OSS

to be around 4-5 points for patients with shoulder conditions (32, 33). The observed SD of the OSS at 12

and 24 months in the CSAW & UKUFF trials was 9 & 8 points respectively (3, 34) To detect a target

difference of 4 OSS points & assuming a SD of 9 with 2- sided 5% significance level & 90% statistical power,

requires 108 participants per group (216 overall). Allowing for 20% attrition (16% observed in the UKUFF

trial at 24 months) (3) (the final sample size is 135 per group (270 overall). Allowing for 30% ineligibility in

theatre at time of arthroscopy means 386 patients will be recruited.

11.4. Analysis populations

The main analyses (to be conducted once the 24 months data is available) will be according to randomised

groups irrespective of non-compliance, "as randomised" population. This is akin to intention to treat or a

treatment policy population; however, no imputation of missing data will be carried out under the main

analyses. For complications and further surgery an "as treated" population where individuals will be

grouped according to whether they received ADAR or ADO will also be used. An "as randomised"

population summary will also be produced.

Clinical Research Protocol Template version 15.0

11.5. Stopping rules

An independent Data Safety Monitoring Committee (DSMC) will meet early in the course of the trial to

agree terms of reference and will review confidential interim reports of accumulating data. No formal

stopping rules are incorporated and accordingly no formal interim analyses planned.

11.6. The Level of Statistical Significance

The statistical significance will be assessed at 5% for two-sided tests and reported for p-values less than

5% (p values of less than 0.05). All p values will be reported to 3 decimal places. 95% confidence intervals

will be reported throughout. Subgroup analyses will be considered exploratory though nominally at the

same 2-sided 5% significance level.

11.7. Procedure for Accounting for Missing, Unused, and Spurious Data

The number and percentage of individuals in the missing category will be presented by treatment arm. No

data will be considered spurious in the analysis since all data will be checked and cleaned before statistical

analyses. Prior to any statistical analysis, missing data pattern will be investigated and reasons for missing

data obtained and summarised where possible. The impact of missing data on the findings will also be

explored in a sensitivity analysis (see Section 11.2)

11.8. Procedures for Reporting any Deviation(s) from the Original Statistical Plan

Substantive deviations from the original SAP will be documented in the statistical report and justification

for each deviation provided.

12. OTHER ANALYSES

12.1. Imaging and diagnostic uncertainty analyses

Descriptive statistics will be used to report the total number (%) of patients where PTT is not confirmed

during arthroscopy (false positive rate for MRI), overall and for each participating site. The characteristics

of this group of ineligible patients will be described and compared with those who were eligible for the

trial. Logistic regression will be used to explore for any patient and disease characteristics associated with

the probability of a false positive result from imaging.

False positive rates (proportions of ineligible patients with no tear, FTT or PTT less than 50% tendon

thickness) as well as trial recruitment rates will be graphically presented for the 24-month recruitment

period to visually present trends and fluctuations over time. Joinpoint regression will used to determine

the mean monthly percentage change in false positive rates and recruitment rates over time and to assess

if a significant change occurred at 12 months, after targeted feedback to those recruiting centres with

higher false positive rates.

## 12.2. Health Economics Analysis

The cost-effectiveness of ADAR compared to ADO will be assessed by a full within-trial economic evaluation where both relevant costs and outcomes for each alternative will be considered. As the main statistical analyses, the economic analysis will be performed according to randomised groups irrespective of non-compliance, "as randomised" or "as allocated" population, i.e. on an intention-to-treat basis. The economic evaluation will follow a Health Economics Analysis Plan (HEAP) agreed in advance by the TSC. The analysis will be conducted from an NHS and personal social services perspective to estimate the relative difference in healthcare costs and quality-adjusted life years (QALYs) between the two arms of the trial. Costs will mainly include primary and hospital healthcare services collected via CRFs and resource use questionnaires at six, 12 and 24 months. Benefits will be reported in terms of QALYs, which will be calculated from answers to the EQ-5D questionnaire and the corresponding social value set of preferences. Although there are no definitive set of valuations for the health states in the EQ5D-5L questionnaire for England or the UK yet, the most up-to-date position statement from NICE (35) suggests using the EQ5D-5L and an algorithm to map to 3L valuations (36). We will use the most up-to-date recommendation on how to value health states measured using the EQ5D-5L instrument at the time of analysis. The valuation will allow to produce health utility estimates at baseline, six, 12 and 24 months, with QALYs estimated using the area under the curve method. Given the number and nature of resource use data collection methods and time points, we expect some missing data in both costs and outcomes. Multiple imputation methods will be used as the base case analyses to impute missing cost and QALY data and avoid biases associated with a complete case analysis.

The results of the economic evaluation will be reported in terms of incremental net monetary benefits using the NICE recommended thresholds of £20,000 and £30,000 per QALY. If no arm is dominant (i.e., reporting both lower costs and better outcomes), we will also report the incremental cost-effectiveness ratio (ICER), i.e. the additional cost per QALY gained by undertaking ADAR compared to ADO. We will consider producing results by subgroups if specific subpopulations such as by demographic (e.g. age) or clinical characteristics are found to be relevant and if allowed by statistical power. Sensitivity analyses will be conducted to explore the implications of uncertainty around key inputs in the analysis. As a sensitivity analysis, the economic evaluation will be conducted from the societal perspective (i.e. including costs for absenteeism from work).

For the long-term (five-year) analysis, cost-effectiveness will be assessed based on hospital costs obtained from routinely HES collected data and long-term health-related quality of life (EQ-5D-5L) collected at 5 years follow-up following the procedures in each trial arm. A series of sensitivity analyses will be undertaken to explore the implications of uncertainty around the costing and methodological assumptions on overall results.

Clinical Research Protocol Template version 15.0

12.3. Qualitative Data Analysis

All qualitative data will be audio-recorded using digital encrypted recorders, transcribed verbatim and

edited to ensure anonymity of respondent. Interview data will be managed using NVivo software (QRS

International) and analysed thematically using constant comparative approaches derived from Grounded

Theory methodology. Consultation data will be analysed using novel approaches, including targeted

conversation analysis (37) and appointment timing (the 'Q-Qat method') (38). There will be a focus on

aspects of information provision that are unclear, disrupted, or potentially detrimental to recruitment

and/or adherence. Analysis will be led by the qualitative researcher, with a sample of transcripts

independently coded by a second qualitative methodologist.

12.4. HES 5-year Data Analysis

The effect of treatment on HES-based outcomes will be analysed separately in the linked dataset by

members of our group with specific expertise in such analyses.

A HES working dataset will be produced by a senior data manager with expertise in such procedures. Under

supervision from the application team, the data manager will develop ad-hoc code in Python and SQL to

produce a dataset that can be analysed using standard statistical packages such as Stata. This will be

carried out using pseudo-anonymised linked datasets.

Outcomes of interest in this long-term data analysis will be analysed as time-to-event data, and will include

all related hospital admissions and procedures, including further surgery and any associated complications

requiring hospital admissions. Patients will be followed up from randomisation to the earliest of each of

the events of interest, death, loss to follow-up (e.g. migration out of England) or 5 years after

randomisation. Incidence rates and 95% confidence intervals and 5-year cumulative incidence will be

estimated stratified by treatment allocation (intention-to-treat/"as allocated') and separately by actual

receipt of the allocated intervention (per protocol). The non-randomised group will be followed up in a

similar way 5 years post intervention to assess the subsequent impact of diagnostic errors (false positive

findings) on rates of any further shoulder surgery.

Finally, Cox regression models will be fitted to estimate Hazard Ratios (HR) and 95 % Confidence Intervals

according to treatment allocation in an intention-to-treat analysis. Similar analyses but with HR estimated

using a "per protocol" population will be conducted. Separate models will be fitted for each of the events

of interest. The proportionality of hazards assumption will be tested using visual inspection of Nelson-

Aalen plots and formal testing using the Schöenfeld's residuals test. Competing risk modelling (cause-

specific Cox) will be conducted if there is evidence of substantial differential mortality between treatment

groups.

#### 13. DATA MANAGEMENT

The data management aspects of the study are summarised here with details fully described in the Data Management Plan.

[figure not shown]

Figure 4: Data Flow Diagram

## 13.1. Source Data

Source documents are where data are first recorded, and from which participants' CRF data are obtained. These include, but are not limited to, hospital records (from which medical history and previous and concurrent medication may be summarised into the CRF), clinical and office charts, laboratory and pharmacy records, diaries, microfiches, radiographs, and correspondence.

CRF entries will be considered source data if the CRF is the site of the original recording (e.g. there is no other written or electronic record of data). All documents will be stored safely in confidential conditions. On all study-specific documents, other than the signed consents, the participant will be referred to by the study participant number/code, not by name.

